CLINICAL INVESTIGATION PLAN (CIP)

The HEURISTIC Study

HErnia RedUction PRIor to Scheduled TIF Completion

This document complies with requirements of the Declaration of Helsinki, International Harmonized Standards: EN ISO 14155-1 and ISO 14155-2:2003(E) and with 21 CFR Parts 50, 54, 56, and 812.

Sponsor: EndoGastric Solutions, Inc.
[name]
[name]
[contact]

Study Responsibility: Investigator Initiated
Each study investigator is responsible for institutional and protocol compliance

CRO Daniel & Daniel Consulting, LLC
<http://www.clinregconsult.com>

Principal Investigator: [name].
Northern Nevada Medical Group
[name]
[name]

CO- Investigators: [name] (Iron River Hospital, Iron River, MI) [name] ([Indiana Medical Research, Elkhart, IN](#))

Date of Issue: December 19, 2017

This protocol contains confidential information for use by the Investigators and their designated representatives participating in this clinical investigation. It should be held confidential and maintained in a secure location.

Do not copy or distribute without written permission.

Protocol Approval Page

STUDY TITLE: HErnia RedUction PRIor to Scheduled TIF Completion
- The HEURISTIC Study

PROTOCOL NUMBER: D031517

VERSION NUMBER: C

DATE: December 19, 2017

We, the undersigned, have read and approve the protocol specified above and agree on its content.

[name]

Date:

[name]

CRO

Date:

Investigator's Signature Page

STUDY TITLE: HErnia RedUction PRIor to Scheduled TIF Completion
- The HEURISTIC Study

STUDY CENTER:

(Print name of study center)

We, the undersigned, have read and understand the protocol specified above and agree on its content.
We agree to perform and conduct the study as described in the protocol.

Investigator

Date

Print name:

Investigator

Date

Print name:

Investigator

Date

Print name:

Investigator

Date

Print name:

Protocol Synopsis

The HEURISTIC Study

HErnia RedUction PRIor to Scheduled TIF Completion

Primary Objective	Evaluation of the relative merits, safety and effectiveness of the EsophyX ZR transoral device in performing the standardized TIF 2.0 procedure preceded by laparoscopic Hiatal Hernia repair in PPI-prescribed patients with persistent “troublesome symptoms” per the Montreal consensus definition.
Test Device	EsophyX ZR System
Principal Investigator	[name]. Northern Nevada Medical Group [name] [name]
Co-Investigators	, [name] (Iron River Hospital, MI) [name] (Elkhart Hospital, IN)
Type of Study	Prospective, investigator initiated, multicenter, non-randomized single arm, open label.
Study Duration	6 Months for primary endpoint. 1 and 2 year follow-up for QOL per SOC.
Number of Patients Number of Sites	50 patients from 3 sites
Follow-Up Schedule	Following TIF procedure, patients will be expected to complete follow-up visits at the 2-Week, 3-Month, and 6-Month time points. Additional follow-up to be completed at 12 and 24 months to assess long-term symptom relief. Consideration will be given to extending follow-up with questionnaires to 3, 4 and 5 years. The study will be considered complete (with regard to the primary effectiveness endpoint) after all patients have completed the 6-Month follow-up visit.

Inclusion Criteria	
 1. Age 18-80 years 2. Dependent upon daily PPIs for > 6 months. Daily use is defined as a double dose, or full dose or half dose taken daily for more than 80% of the total number of days during the proceeding evaluation period 3. Troublesome symptoms, specifically heartburn or regurgitation, while on optimized dose of PPI's Troublesome heartburn or regurgitation symptoms are those which occur a minimum of 2 days a week and are mild to severe in severity 4. Abnormal ambulatory (Bravo) pH study after off PPI therapy for 7 days, i.e. > 5.3% of the time with pH < 4 in a 48-hour monitoring period 5. Normal or near normal esophageal motility (by Upper GI/ esophagram or manometry as required) 6. Pre-enrollment Hiatal Hernia (axial height and transverse dimension) from > 2 cm up to 4 cm inclusive. 7. Patient willing to cooperate with post-operative dietary recommendations and assessment tests at the requisite follow-up visits 8. Signed informed consent
Pre-enrollment Exclusion Criteria	
 1. BMI > 35 2. Hiatal hernia \leq 2 and > 4 cm 3. Esophagitis Los Angeles grade C or D 4. Esophageal ulcer 5. Esophageal stricture 6. Long-segment Barretts esophagus (Prague: C > 1, M > 3) 7. Esophageal motility disorder 8. Pregnancy or plans for pregnancy in the next 12 months (in females) 9. Immunosuppression 10. ASA > 2 11. Portal hypertension and/or varices 12. History of previous resective gastric or esophageal surgery, cervical spine fusion, Zenker's diverticulum, esophageal epiphrenic diverticulum, achalasia, scleroderma or dermatomyositis, eosinophilic esophagitis, or cirrhosis 13. Active gastro-duodenal ulcer disease 14. Gastric outlet obstruction or stenosis 15. Severe gastroparesis or delayed gastric emptying confirmed by solid-phase gastric emptying study if patient complains of postprandial satiety during assessment 16. Coagulation disorders 17. Atypical symptoms including gas bloat and dysphagia. 18. Any other presenting condition that in the opinion of the investigator would not make participation in this study in the patient's best interest.

Post Enrollment Exclusion	1. Inability to repair Hiatal hernia with at least 2cm of intra-abdominal esophagus length.
Intervention	
Treatment: Standardized Transoral Incisionless Fundoplication (TIF 2.0) using EsophyX ZR system with SerosaFuse fasteners (EndoGastric Solutions, Inc., Redmond, WA, USA) preceded by Hiatal Hernia repair.
 
Control: Each patient will serve as his/her own control (condition prior to HH repair and TIF 2.0)

Evaluation Criteria	
Primary Effectiveness Endpoint: Normalization in esophageal acid exposure is defined by $\leq 5.3\%$ of total time pH < 4 in a 48-hour monitoring period.
 
Secondary Effectiveness Endpoint 1: Per Montreal Consensus definition, troublesome symptoms are mild symptoms occurring two (2) or more days per week, or moderate/severe symptoms occurring more than 1 day per week.
 
Secondary Effectiveness Endpoint 2: Clinically significant PPI consumption reduction is defined as from daily use to occasional use or none at all. Daily use is defined as a double dose, or full dose or half dose taken daily for more than 80 % of the total number of days during the proceeding evaluation period.

Study Hypotheses	
Primary Effectiveness hypothesis At 6-month follow-up, the proportion of TIF patients with normalized esophageal acid exposure will be statistically non-inferior to results from the EGS RESPECT study.
 
Secondary Effectiveness hypothesis 1 The proportion of TIF patients who are free of “troublesome” symptoms will be the same as or higher than the EGS RESPECT study.
 
Secondary Effectiveness hypothesis 2 At 6-month follow-up, $\geq 50\%$ of the TIF patients will have a clinically significant reduction in PPI consumption as compared with their pre-TIF consumption.
 
Primary Safety hypothesis 1 At 6-month follow-up, no increase in medically significant AE's as compared with the RESPECT study
 
Secondary Safety hypothesis 1 At 6-month follow-up, no new onset symptoms and side effects frequently associated with Nissen fundoplication procedures including dysphagia and gas bloat.

-------------------------	---

Table of Contents

Protocol Approval Page	2
Investigator's Signature Page	3
Table of Contents.....	8
1. Introduction and History of Prior Investigations.....	11
2. Device Description	13
3. Study Design Rationale	14
4. Study Objective	15
5. Study Hypotheses	15
5.1. Primary Efficacy Hypothesis 1.....	15
5.2. Secondary Efficacy Hypothesis 1	15
5.3. Secondary Efficacy Hypothesis 2.....	15
5.4. Primary Safety Hypothesis 1	15
5.5. Secondary Safety Hypotheses 1	16
6. Study Design	16
6.1. Study Population.....	16
6.2. Study Schematic Design.....	16
7. Study Population	18
7.1. Selection Criteria	18
7.2. Withdrawal	19
8. Study Methods and Techniques	19
8.1. Clinical Symptom Assessments.....	19
8.2. PPI Usage	19
8.3. Upper GI Endoscopy	20
8.4. BRAVO pH Studies.....	21
8.5. Esophageal Motility.....	21
9. Study Procedures	21
9.1. Determination of Patient Eligibility – Screening Process	23
Initial Screening -	23
Final Screening :-	23
9.2. Prior to the Study Procedure.....	23
9.3. During the Study Procedure	23
TIF Procedure (Treatment).....	24
9.4. Post-Procedure / Hospital Discharge	25
9.5. Follow-up.....	25
10. Statistical Considerations	26
10.1. Analysis Populations and Missing Data Handling	26
10.2. Statistical Analysis Plan	26
10.1. Sample Size and Power Estimation	27
11. Clinical Effectiveness Endpoints and Evaluation Criteria	27

11.1. Clinical effectiveness.....	27
12. Risks	28
13. Adverse Events.....	29
13.1. Causality and Seriousness Assessment.....	29
13.2. Reporting Serious Adverse Events	30

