Historically, clinical results, with patients presenting with $\leq 2\text{cm}$ hiatal hernias, have demonstrated that the TIF procedures using the EsophyX system with SerosaFuse fasteners is effective in eliminating symptoms, decreasing the need for daily PPIs, normalizing esophageal acid exposure, increasing LES resting pressure, and promoting healing of esophagitis in more than 80% of patients with chronic GERD. The obtained improvement in clinical and pathophysiological outcomes correlated significantly with the quality of the anatomic reconstruction. This clinical study is designed to explore use of the TIF procedure in patients who have had their hiatal hernias reduced from between $>2\text{cm}$ and $\leq 4\text{ cm}$ to $\leq 2\text{cm}$. Demonstration that TIF results with these patients are similar to TIF results from patients initially presenting with $\leq 2\text{cm}$ hiatal hernias while avoiding traditional NF complications could provide expanded patient choices in the minimally invasive treatment of GERD.

¹ Neuvonen, Perttu, Mauri Iivonen, and Tuomo Rantanen. "Endoscopic evaluation of laparoscopic nissen fundoplication: 89% success rate 10 years after surgery." *World journal of surgery* 38.4 (2014): 882-889.

[figure not shown]
² Waring JP (1999). "Postfundoplication complications. Prevention and management". *Gastroenterol. Clin. North Am.* 28 (4): 1007–19, viii–ix. doi:10.1016/S0889-8553(05)70102-3. PMID 10695014.

	RESPECT¹⁶	TEMPO^{17,18,19}	TIF vs. Sham²⁰	TIF Registry^{21,22,23}	STAR Registry
Design	A multi-center, randomized, single-blind, controlled TIF/Placebo vs. Sham/PPIs trial	A multi-center, randomized, open-label, controlled TIF vs. PPI trial	A multi-center, double-blind, sham controlled randomized trial	A multi-center, prospective, open-label, post market registry	An AGA-sponsored, multi-center, prospective, open-label, post market registry
Objective	To compare safety and effectiveness of TIF vs. Sham/PPIs in patients with “troublesome symptoms” specifically regurgitation	To compare safety and efficacy of TIF vs. PPIs for the treatment of chronic medically refractory GERD	To gauge the time to ‘treatment failure’ during the first 6 months after intervention	To evaluate the safety and efficacy of TIF in a broad range of GERD patients treated in routine clinical practice	To compare the safety and efficacy of TIF procedure vs. Laparoscopic Nissen Fundoplication Surgery (LNF)

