Patients	2:1 ratio TIF/Placebo group (n=80) vs. Sham/PPI group (n=40)	2:1 ratio TIF group (n=28) vs. PPIs group (n=14)	1:1 ratio TIF group (n=22) vs. sham group (n=22)	274 patients treated with TIF procedure	1:1 ratio TIF group (n=250) vs. LNF group (n=250)
Duration(s)	6 months, 1 year w/ crossover (abstract)	6 months, 1 year w/ crossover, 3 years	6 months	6 months, 1 year, 2 years	Ongoing
Key Outcomes	
 ✓ Troublesome regurgitation was eliminated in 72% of TIF patients at > 1Y ✓ Median heartburn score decreased from 17 to 5 at 6 months and to 3, at > 1Y post-TIF ✓ Complete cessation of PPI therapy was achieved in 72% of TIF patients > 1Y 	
 ✓ All symptomatic outcome measures were stable between 1Y, 2Y and 3Y follow-up ✓ Esophagitis was healed in 86% of patients at 3Y follow-up ✓ 71% of patients completely off PPIs at 3Y follow-up ✓ Improvement in pH parameters remained stable at 3Y follow-up 	
 ✓ Average of 197 days “time in remission” post-TIF vs. 107 days post-sham ✓ Six months post-op 13/22 (59%) of TIF patients were in clinical remission with complete cessation of PPIs consumption. ✓ 69% of the TIF group normalized esophageal acid exposure vs. 20% of the sham group 	At 2Y follow-up: 
 ✓ 65% normalization in the Reflux Symptom Index score ✓ 74% normalization of Gastroesophageal Reflux Symptom Score ✓ A decrease from 91% to 29% in daily PPI use ✓ 75% of patients had esophagitis healed 	In enrollment

Table 2. Summary of Level I and II Clinical Studies (TIF 2.0)

2. Device Description

The EsophyX® Z device is a single use, hand-held flexible instrument that is introduced transorally with a flexible endoscope in the center of the device, so the entire procedure can be done safely under direct visualization. The device is designed so the physician can manipulate esophageal and gastric tissue, creating a partial fundoplication, secured by and deploy strong, H-shaped fasteners in order to reconfigure lower esophageal anatomy to prevent GERD.

3. Study Design Rationale

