The study population will consist of patients with chronic “troublesome” GERD symptoms while on PPIs and proven anatomic deterioration of the gastroesophageal junction who prefer a laparoscopic Hiatal Hernia Repair followed by an endoscopic intervention (TIF 2.0) over the long term treatment of PPIs. These patients should have well documented GERD with or without endoscopic signs of esophagitis, hiatal hernia >2cm and up to 4 cm and a history of > 6 months of daily use of PPI to control major GERD symptoms.

6.2. *Study Schematic Design*

Please see next page.

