Study Endpoints/Outcomes	Control	Pre-procedure Value	Post-procedure Value	Success Criteria
PRIMARY EFFECTIVENESS				
Normalized acid exposure	Self-Comparison	BRAVO Ph studies after off anti-secretory meds ≥ 7 days	BRAVO Ph studies at 6 months after off anti-secretory meds ≥ 7 days	Treatment success will be defined by a proportion of TIF patients with normalized acid exposure that is non-inferior to the RESPECT result as defined in 10.2.2.
SECONDARY EFFECTIVENESS				
GERD symptoms	Self-Comparison	Reflux Disease Questionnaire (RDQ) scores	Reflux Disease Questionnaire (RDQ) scores at and 6 months	Treatment success will be defined by a proportion of TIF patients free of troublesome symptoms at 6 months that is \geq the same proportion in RESPECT Trial (67%)
PPI usage	Self-Comparison	PPI usage (must be "daily")	PPI usage at 6 months	Treatment success will be defined by $\geq 50\%$ of TIF patients that has a clinically significant reduction, i.e. from "daily" PPI use to "none" or "occasional" use, at 6 months.

12. Risks

The following risks are anticipated and can result from the TIF procedure or general anesthesia:

Expected typical risks or discomfort:

- Pharyngolaryngeal pain (e.g., sore throat)
- Musculoskeletal pain (e.g., left shoulder pain)
- Temporary epigastric or abdominal pain, which can be treated with standard pain medication
- Temporary dysphagia (i.e., difficulty swallowing) due to swelling
- Nausea or vomiting

Unusual risks or discomfort:

- Oral or dental injury
- Bleeding
- Bloating sensation
- Hematoma

Rare risks:

- Esophageal perforation, laceration or tear
- Aspiration, hypoxia, achalasia

- Nerve damage
- Arrhythmia
- Pneumothorax, chest pain
- Pneumoabdomen
- Fistula
- Infection of the mediastinal space

Additional risks:

- Operation to remove a defective device or its parts
- Reoperation after a failed procedure (insufficient symptom relief)

13. Adverse Events

All adverse events will be monitored from the time of enrolling through the 6-month follow-up visit. Unanticipated adverse device effects (UADE) and SAEs will be monitored through the 12-month follow-up.

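### Table 5 declares symptom success when an open-label, self-reported 6-month rate reaches RESPECT's 67%, with no margin and no allowance for differences in blinding, endpoint or hernia size

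*Combined protocol and SAP*

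**What the plan says.** The synopsis describes HEURISTIC as "Prospective, investigator initiated, multicenter, non-randomized single arm, open label". Section 6.1 takes patients "who prefer a laparoscopic Hiatal Hernia Repair followed by an endoscopic intervention (TIF 2.0) over the long term treatment of PPIs".

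Secondary effectiveness hypothesis 1, in the synopsis and again in 5.2, is that the proportion free of troublesome "symptoms will be the same as or higher than the EGS RESPECT study". Neither statement gives a timepoint, a benchmark figure, a margin or a significance level. Table 5 supplies the timepoint and the figure. It scores the endpoint from the Reflux Disease Questionnaire (RDQ) and defines treatment success as a 6-month proportion no lower than "the same proportion in RESPECT Trial (67"%). Table 5 lists the control for this row as self-comparison, although the success criterion is an external rate.

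Sections 10.2.1 and 10.2.2 plan only a descriptive summary with a 95% confidence interval for this endpoint. The formal non-inferiority test against RESPECT is confined to acid exposure.

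Table 2 describes RESPECT as "A multi-center, randomized, single-blind, controlled TIF/Placebo vs. Sham/PPIs trial", in a "2:1 ratio TIF/Placebo group (n=80) vs. Sham/PPI group (n=40"), and gives its symptom target as troublesome symptoms, "specifically regurgitation". Section 11.1 defines the HEURISTIC endpoint as freedom from troublesome heartburn and/or regurgitation.

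**The concern.** The RDQ (Appendix E) is a tick-box form on which patients rate the frequency and severity of their own symptoms. HEURISTIC patients know they have had both the hernia repair and the fundoplication, and were enrolled because they preferred that course to continued PPIs. Their answers are set against a rate from a trial whose placebo and sham suggest that patients did not know their allocation. Expectation can therefore lift the HEURISTIC rate without any difference in what the procedure does. The primary endpoint, a capsule pH measurement, is not self-reported and is not exposed in this way.

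The rule has no protection against this. It compares one observed proportion with one fixed number, with no margin, no test and no use of the planned interval. Followed as written, it yields a statement that symptom relief matches RESPECT, which the comparison cannot support.

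**Working it through.** **The plan's own figure.** The only power stated is for the primary endpoint. With n = 50, null rate 24%, true rate 44% and success at 18 or more, the exact binomial gives P(X ≥ 18 | 0.24) = 0.038 and P(X ≥ 18 | 0.44) = 0.901. This agrees with the stated 0.90. (17/50 would give 0.072, so 18 is the correct threshold at one-sided 0.05.) The documents state no threshold count, error rate or power for the symptom rule, so these have to be derived.

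**Inputs for the symptom rule.** 50 patients (synopsis); benchmark 67% at 6 months, met by the observed proportion (Table 5); available data, no imputation (10.1).

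**Threshold.** 0.67 × 50 = 33.5, so at least 34 of 50 are needed, which is 68%.

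**Precision at the threshold.** The exact (Clopper-Pearson) 95% limits for 34/50 are the 2.5% point of Beta(34, 17) and the 97.5% point of Beta(35, 16): 53.3% to 80.5%. A result that just passes is compatible with a rate about 14 points below the benchmark (67 − 53.3 = 13.7).

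**Chance of passing.** P(X ≥ 34) with X ~ Binomial(50, p), where p is the true rate plus an upward reporting shift. The true rate here means the rate patients would report under RESPECT's conditions. The documents give no size for an expectation effect, so every shift is an assumption and a range is shown.

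| True rate | No shift | +5 points | +10 points | +15 points |
|---|---|---|---|---|
| 67% (equal to RESPECT) | 0.507 | 0.787 | 0.949 | 0.995 |
| 62% | 0.235 | 0.507 | 0.787 | 0.949 |
| 57% | 0.075 | 0.235 | 0.507 | 0.787 |
| 52% | 0.016 | 0.075 | 0.235 | 0.507 |

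The table also reads the other way. If the stricter endpoint and larger hernias lowered the reported rate by a net 5 points, a procedure equal to RESPECT at 67% would be reported at 62% and would pass with probability 0.235 instead of 0.507. The rule's answer moves substantially with a modest shift in either direction.

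**Fewer evaluable patients.** With 45 evaluable the bar is 31 (0.67 × 45 = 30.15), and a true 62% passes with probability 0.214, 0.463 or 0.741 at shifts of 0, 5 or 10 points. With 40 the bar is 27 (0.67 × 40 = 26.8), and the figures are 0.293, 0.548 and 0.794. The pattern does not depend on reaching exactly 50.

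**Uncertainty in the benchmark.** The documents give no denominator for the 67%. If it came from all 80 TIF patients in Table 2 (assumed; 54/80 = 67.5% is the nearest count), its own exact 95% interval would be about 56.1% to 77.6%. The rule treats it as known.

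**How the two rates differ.**

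- Blinding: HEURISTIC is open label; RESPECT was single-blind with placebo and sham. Effect on HEURISTIC's reported rate: probably upward.
- Endpoint: HEURISTIC counts heartburn and/or regurgitation; RESPECT targeted regurgitation. Being free of both may be harder, so the effect may be downward.
- Hernia size: HEURISTIC enrols hernias above 2 cm and up to 4 cm. Section 1 describes the historical TIF results as coming from hernias of 2 cm or less, though Table 2 does not give RESPECT's limit. Direction unknown.
- Procedure: HEURISTIC adds a laparoscopic repair. Direction unknown.

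**The case against.** **The plan is already descriptive.** Sections 10.2.1 and 10.2.2 give this endpoint a proportion and an interval, and the only formal RESPECT test is on pH. That is true, and it limits the consequences. But Table 5 still attaches a binary success label to the point estimate and the hypothesis claims parity with RESPECT, so the reported conclusion would follow from those.

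**The bias is not shown to run one way.** A reader might infer that open-label reporting makes the rule biased towards success overall, or that expectation alone would deliver it. The documents do not support this. The endpoint and hernia differences may pull the other way, and Table 2 does not say what RESPECT patients preferred, so the selection in 6.1 cannot be called a difference between the trials. Nor is the bar easy to clear: without any shift, a procedure equal to RESPECT passes only about half the time (0.507). This objection stands. What remains is that the 67% is not a like-for-like benchmark.

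**Patient blinding and 6-month timing are inferred.** Table 2 says single-blind without naming who was blinded; the placebo and sham point to the patients. Table 5 does not date the 67%; its wording implies the matching 6-month proportion. Both readings are reasonable but not stated.

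**A later RESPECT figure might seem a fairer benchmark.** Table 2 also reports "Troublesome regurgitation was eliminated in 72% of TIF patients at > 1Y", and a reader might take this as an open-label rate to compare with HEURISTIC at 12 months. The documents do not support that use. They do not say the blind had ended. The figure follows crossover, covers regurgitation only and has no denominator. HEURISTIC's 12-month RDQ is completed off PPIs, and Table 2 does not say RESPECT's was. The comparison would also still set a point estimate against a historical rate without a margin.

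**Conclusion.** The concern holds in a limited form. As written, Table 5 and the matching hypothesis allow a conclusion of symptom relief equal to RESPECT from a comparison that differs in blinding, in the symptoms counted and probably in hernia size, by a rule with no margin and no allowance for sampling error in either rate. With 50 evaluable patients, 34/50 passes although its 95% interval reaches down to 53.3%. A true rate of 62% passes with probability 0.235, and with 0.507 or 0.787 under reporting shifts of 5 or 10 points.

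The threshold, the interval and the no-shift probabilities follow from the protocol's numbers, taking all 50 patients as evaluable. The shifts are assumptions, and patient blinding and the 6-month timing of the 67% are inferences. The net direction of bias is not established. The endpoint is secondary, and the primary pH conclusion is unaffected.

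**What to change.** Change the wording in three places: the synopsis (secondary effectiveness hypothesis 1), 5.2 and Table 5.

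- Remove equality with, or superiority to, RESPECT's 67% as a hypothesis and success criterion.
- State that the 6-month proportion free of troublesome symptoms will be estimated and reported with its 95% confidence interval. Section 10.2.2 already provides for this and need not change.
- If the 67% is shown, present it as context only. State beside it that it comes from a single-blind trial with placebo and sham, that RESPECT targeted regurgitation while HEURISTIC counts heartburn and/or regurgitation, and that HEURISTIC enrols hernias above 2 cm. Confirm from the RESPECT report who was blinded, the timepoint and the denominator.
- Rest any RESPECT-based effectiveness claim on the pH endpoint, for which 10.2.2 defines a margin and an exact test.
- Do not substitute a 12-month comparison with the 72% figure.

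The cost is an edit to the text. No data, visits or patients are added. The sponsor gives up one secondary success claim.
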